11. DATA ANALYSES

The primary variable for inferential statistics is VTE. Based on available data and pharmacological/pharmacokinetic considerations the *a priori* assumption is that use of DRSP/EE+ is not associated with an increased risk of VTE compared to established OCs. That is, a statistical comparison of DRSP/EE+ and established OCs is not expected to show a difference. Therefore, a non-inferiority design to investigate the VTE risk of DRSP/EE+ was chosen. The primary analysis will be based on the comparison of the upper confidence limit for the point estimate of the VTE hazard ratio with the predefined non-inferiority limit (cf. section 12).

The null hypothesis to be tested is: $HR_{VTE} \geq 2$ (i.e., the VTE hazard ratio for DRSP/EE+ vs. established OCs is higher or equal to 2). The alternative hypothesis is: $HR_{VTE} < 2$.

Sub-analyses will include COC+, DNG/EE+, specific regimens of DRSP/EE+ (e.g., the 24-day regimen of 3mg DRSP/20µg EE) as well as starters and recurrent user with and without pill-intake break.

Safety monitoring during study conduct will be based primarily on the ITT analysis of crude data. The final analyses will include both an “as treated” (AT) and an intention-to-treat (ITT) analysis using Cox regression models. The safety conclusions of the study, however, will be based on the AT analyses because the ITT approach potentially dilutes differences between treatments.

Crude as well as adjusted hazard ratios will be calculated. The appropriate confounding variables will be built into the statistical model. Based on the expectation of a small absolute number of serious outcomes of interest the number of confounding variables will be limited to well established risk factors for these outcomes. For VTE/ATE these will include age, BMI, duration of current use, and VTE history. For Colorectal cancer age, BMI, alcohol intake and family history of CRC are planned. The final decision on the confounding variables will be made by the Safety Monitoring and Advisory Council before the first interim analysis of follow-

up data. In addition, alternative analysis will be performed with other potential baseline risks to check the appropriateness of this decision. Similar analyses will be performed for arterial thromboembolism (e.g., acute myocardial infarction and stroke), colorectal cancer and other serious adverse events.

A detailed statistical analysis plan will be developed by the Principal Investigator during the first year after study start. The final analysis plan will be approved by the Safety Monitoring and Advisory Council before the first interim analysis of follow-up data.

Within the first 5 years biannual interim reports will be provided to the funder following release of the interim analyses results by the independent Safety Monitoring and Advisory Council (cf. section 13). In the following years annual reports will be provided.

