5. STUDY PARTICIPANTS

The study participants are women who

- are new users of an OC (first ever use, recurrent use with and without pill break)
- are willing to participate in this long-term follow-up study

⁴ planned follow-up for an individual patient at least 12 years, but can be longer based on time point of study entry. (cf. section 7)

Women will be categorized into three different groups depending on OC-user characteristics. These groups have been previously found to be important in assessing cardiovascular risk [31]. The groups are defined as 1) OC starters (first-time users), 2) recurrent users with a break (re-starters and switchers with a break) and 3) recurrent users without a pill-intake break.

There are no specific medical inclusion or exclusion criteria. However, women

- who are not cooperative/available for follow-up may be excluded from study participation
- with a language barrier will not be eligible for study inclusion

At the participating centers, all women seeking a prescription for a new OC are to be asked by their physician if they are willing to participate. The physician is to explain the nature of the study, its purpose and associated procedures, and the expected duration of follow-up for each woman prior to her study entry. Each woman is to have ample opportunity to ask questions and must be informed about her right to withdraw from the study at any time without disadvantage and without having to provide reasons for her decision. This information will be provided on an informed consent and data privacy form which must be signed by all study participants. These documents are to be approved by the relevant local Ethics Committees and the relevant Data Privacy Office, if applicable.

Once enrolled, a subject may discontinue use of OCs at any time. However, subjects will continue to be followed whether or not they remain on OCs, provided that they do not withdraw their consent. During the follow-up phase, subjects will be asked whether they have discontinued OC use or whether they have switched to another OC preparation. Information on the date and reason for discontinuation or switching during the follow-up phase will also be collected.

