3	20,501	21,640	22,779	24,045	25,310	12,913
4	18,451	19,476	20,501	21,640	22,779	24,045
5	16,606	17,529	18,451	19,476	20,501	21,640
6	15,444	16,025	16,606	17,529	18,451	19,476
7	14,363	14,903	15,444	16,025	16,606	17,529
8	13,357	13,860	14,363	14,903	15,444	16,025
9	12,422	12,890	13,357	13,860	14,363	14,903
10	11,553	11,987	12,422	12,890	13,357	13,860
11	10,975	11,264	11,553	11,987	12,422	12,890
12	10,426	10,701	10,975	11,264	11,553	11,987
13	9,905	10,166	10,426	10,701	10,975	11,264
14	9,410	9,657	9,905	10,166	10,426	10,701
15	8,939	9,174	9,410	9,657	9,905	10,166
16	8,492	8,716	8,939	9,174	9,410	9,657
WY (total)		224,946		216,230		207,056
WY (grand total)	648,232					

* Time after start of recruitment

** The number of recruited women equals 26,667. However, the number of women at the end of the first year is lower because some women will drop out during the first year (daily drop-out rate for follow-up years 1-5: ~ 0.029%, for years 6-10: ~ 0.020%, for years 11+: ~ 0.014%).

Overall, it is expected that the observation time in the study will be in the range of 620,000 WY (up to 15 years of follow-up) and 650,000 WY (up to 16 years of follow-up).

Evaluation part I

An evaluation of the cardiovascular events will take place 5 years after study start. In Table 2 are the total women-years shown which will be observed at that point in time. Based on the results of EURAS-OC [1], it is assumed that at that point in time about 4/5 of the observed time represents exposure time. Therefore, 232,000WY will result in approx. 185,000WY of OC exposure 5 years after study start.

Table 2: Expected observation time for cardiovascular risk (5 years): Patient recruitment within 3 years (annual recruitment rate = 26,667 women)

Time (y)*	Sub-cohorts recruited during the					
	1 st study year		2 nd study year		3 rd study year	
	No. of women	Time of observation	No. of women	Time of observation	No. of women	Time of observation
1	25,310	12,912				
2	22,779	24,044	25,310	12,913		
3	20,501	21,640	22,779	24,045	25,310	12,913
4	18,451	19,476	20,501	21,640	22,779	24,045
5	16,606	17,528	18,451	19,476	20,501	21,640
WY (total)		95,600		78,074		58,598
WY (grand total)	232,272					

* Time after start of recruitment

** The number of recruited women equals 26,667. However, the number of women at the end of the first year is lower because some women will drop out during the first year (daily drop-out rate ~ 0.029%).

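### Interim safety monitoring rests primarily on crude ITT data, while the same paragraph bases the safety conclusions on AT because ITT may dilute differences

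*Protocol*

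**What the plan says.** Protocol section 11 fixes the monitoring analysis: "Safety monitoring during study conduct will be based primarily on the ITT analysis of crude data". For the end of the study it says: "The final analyses will include both an “as treated” (AT) and an intention-to-treat (ITT) analysis using Cox regression models". It then ranks the two: "The safety conclusions of the study, however, will be based on the AT analyses because the ITT approach potentially dilutes differences between treatments".

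Three other statements bear on this.
- Section 5 keeps women under observation after they stop: "However, subjects will continue to be followed whether or not they remain on OCs, provided that they do not withdraw their consent".
- Section 5 also provides the data needed for an AT analysis: "Information on the date and reason for discontinuation or switching during the follow-up phase will also be collected".
- Section 12 (Evaluation part I) puts the exposed part of follow-up five years after study start at about four fifths: "it is assumed that at that point in time about 4/5 of the observed time represents exposure time".

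No section explains why ITT leads in monitoring when AT leads for the conclusions.

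**The concern.** The reason given for preferring AT at the end applies at least as strongly to interim monitoring. ITT counts time after stopping, and time after switching to another OC, under the starting product. If DRSP/EE+ carries an excess VTE risk, both kinds of time bring the observed hazard ratio closer to 1.

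Using crude data is a separate matter. It leaves the comparison open to confounding, which can act in either direction.

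At stake is how likely the Safety Monitoring and Advisory Council is to see a real VTE excess before the five-year cardiovascular evaluation. The protocol promises an AT comparison only for the final analyses. Because section 11 itself fixes the monitoring basis, this is not simply a detail left to the analysis plan.

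**Working it through.** **Plan's own figures.**
- Exposure: 0.8 × 232,000 = 185,600 WY, which agrees with the stated figure of about 185,000 WY.
- Table 3, 12% share: with k = 0.12/0.88, p = 0.0009 and margin δ = 0.0009, the COC+ requirement is (1.960 + 1.282)² × p(1−p)(1+k)/δ² = 13,255 WY. The printed figure is 13,256.

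**Inputs from the Protocol.** Reference VTE rate 9/10,000 WY; individual product share 7 to 12%; annual drop-out 10% in years 1-5; recruitment over three years. Observed time at study year 3 (Table 2) is 3 × 12,913 + 2 × 24,045 + 21,640 = 108,469 WY.

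**Assumptions, because the Protocol gives no figure.**
- True on-treatment hazard ratio 2.
- VTE rate off OCs: b = 2 to 4 per 10,000 WY.
- Share of the DRSP/EE+ cohort's total time spent on another OC: s = 0 to 0.15. Switching in the other direction is not modelled.
- Illustrative signal: lower 95% limit above 1. The Protocol sets no such rule.

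**Exposed share e at year 3.** The four-fifths figure refers to year 5, so I used two values.
- e = 0.80 applies the year-5 figure unchanged.
- e = 0.88 comes from constant stopping at rate λ. With d = −ln 0.9 = 0.105 and follow-up L, exposed time is (1 − exp(−(d+λ)L))/(d+λ) and observed time is (1 − exp(−dL))/d, both averaged over uniform entry. Setting the year-5 share to 0.80 gives λ = 0.137. The shares at years 1, 2 and 3 are then 0.96, 0.92 and 0.88.
- Mean use of 3 to 4 years, as expected in section 7, would instead give about 0.75 to 0.80 at year 3.

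**Formulas.**
- ITT HR = [(e − s)×18 + s×9 + (1 − e)×b] / [e×9 + (1 − e)×b].
- Chance of a signal = Φ(ln HR / √(1/d1 + 1/d0) − 1.96), with d1 and d0 the expected events.
- For AT, HR = 2 and switched time is counted under the reference.

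**One case in full (12% share, e = 0.80, s = 0.15, b = 4).** Cohort times are 0.12 × 108,469 = 13,016 WY and 95,453 WY.
- ITT: (11.7 + 1.35 + 0.8)/(7.2 + 0.8) = 13.85/8.0 = 1.73. Events are 18.0 and 76.4, so the chance is 55%.
- AT: events are 13,016 × 0.65 × 18/10,000 = 15.2 and 68.7 + 1.8 = 70.5, so the chance is 69%.

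**Results at year 3, 12% share (b = 2 / b = 4; losses taken before rounding).**

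| e | s | ITT HR | ITT chance | AT chance | Loss, points |
|---|---|---|---|---|---|
| 0.80 | 0 | 1.95 / 1.90 | 74% / 72% | 76% | 1.9 / 3.7 |
| 0.80 | 0.05 | 1.89 / 1.84 | 69% / 67% | 74% | 5.0 / 6.9 |
| 0.80 | 0.10 | 1.83 / 1.79 | 63% / 61% | 71% | 8.2 / 10.1 |
| 0.80 | 0.15 | 1.77 / 1.73 | 57% / 55% | 69% | 11.6 / 13.5 |
| 0.88 | 0 | 1.97 / 1.94 | 79% / 78% | 80% | 1.0 / 2.0 |
| 0.88 | 0.05 | 1.92 / 1.89 | 74% / 73% | 78% | 3.6 / 4.7 |
| 0.88 | 0.10 | 1.86 / 1.84 | 69% / 68% | 76% | 6.6 / 7.7 |
| 0.88 | 0.15 | 1.81 / 1.78 | 64% / 63% | 74% | 9.8 / 10.9 |

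At a 7% share and e = 0.80, the chance is 55% / 53% (ITT) against 57% (AT) without switching, and 40% / 39% against 50% with s = 0.15. AT is ahead in every case, although it has fewer events.

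**The case against.** The strongest case against has five parts.

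1. **Monitoring rests only *primarily* on crude ITT.** AT looks are not excluded. Section 11 plans crude and adjusted hazard ratios without confining them to the final analysis, and has the Council settle the confounders and approve the analysis plan before the first interim analysis. This stands. It softens the point but does not explain why the diluted comparison should lead.

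2. **A reader might infer that crude ITT as a whole is biased towards no difference.** The Protocol does not support that. It ties possible dilution to ITT alone, and confounding in unadjusted data can act either way. Section 1 itself argues that bias in two earlier studies overstated the DRSP risk. Only the ITT element has a known direction.

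3. **A reader might also infer that an excess would go unnoticed until year 5.** That is not shown. The Council meets six-monthly during Part I, and interim reports are biannual. Each serious event also gets a causality assessment (section 9), although that is not a comparison between cohorts.

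4. **The larger losses depend on switching, for which the Protocol gives no rate.** This stands: without switching the loss is small. It is smaller still at early looks, where few events limit any analysis. With the declining exposed shares, b = 2 to 4, a 12% share and no switching, the chance of a signal is about 17% under both analyses at year 1 (12,913 WY). At year 2 (49,871 WY) it is 48% for ITT against 49% for AT.

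5. **ITT does not depend on stop and switch dates**, some of which may be unresolved at a given look. That is a good reason to keep it as a companion analysis.

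**Conclusion.** The point holds as an unexplained inconsistency with a modest to moderate effect on signal detection. With a true on-treatment hazard ratio of 2, ITT would show 1.90 to 1.97 without switching and 1.73 to 1.81 with 15% of DRSP/EE+ cohort time on another OC. At study year 3 and a 12% share, the loss against AT is about 1 to 4 points without switching and about 10 to 14 points with 15% switched.

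These sizes rest on the assumed off-OC rate (2 to 4 per 10,000 WY), an exposed share of 80 to 88%, the assumed switching range and an illustrative signal rule. The direction of the ITT effect needs less: it pulls a true excess towards 1 whenever unexposed time carries some VTE risk or women switch. The effect of not adjusting is unknown in direction. The final conclusion, which rests on AT, is not affected. The change is worth making because it is cheap and concerns the detection of harm.

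**What to change.** Amend the monitoring sentence in section 11 so that interim VTE and ATE comparisons for the Council are based primarily on the AT analysis. Show it both crude and adjusted for the covariates section 11 already names for VTE/ATE (age, BMI, duration of current use and VTE history), with crude ITT alongside at each look. Cancer monitoring need not change, since section 12 bases the colorectal cancer calculation on women-years of observation.

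The cost is a little more programming per interim report. Some stop or switch dates may still be under query at the latest look; the ITT results alongside help the Council judge whether that matters. No new data collection is needed.

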7. FOLLOW-UP

A follow-up assessment for each woman is scheduled 6, 12, 18, 24 months after baseline, and then 3, 4, 5, 7½, 10, 12½, 15 years after recruitment. Women will be followed-up for at least 12 years. Women recruited in the early phase of the study will be followed-up until study endpoint [max. 15 years]. During Part II of the study (cf. Section 12) women will be followed-up at 2 ½ yearly intervals. Based on investigator experience from other long-term studies, women who remain in the study for 5 years are likely to remain in the study, even if follow-up periods extend beyond one year.

Follow-up questionnaires will be mailed to the participating women, who often know more about their own personal health related issues than the physician who prescribes their OC. This is especially true for potential adverse events treated by other

physicians. Occasionally, events may be reported by the participant or by a participant's relatives, friends or attending physicians between the regular follow-ups. These reports will be documented and validated in the same way as regular reports (see section 8).

In addition to the follow-up questionnaires, at the 18-month follow-up, a validated food-frequency questionnaire (Dietary Folate Equivalents (DFE) screener) specific for folate intake will be sent to study participants. Folate intake has a relatively stable intra-person variability, particularly in individuals consuming a western diet. In contrast, inter-person variability tends to vary significantly. A single DFE screener during the follow-up period will rank individuals in regard to their average dietary folate intake (inter-person variability) and provide sufficient information for analysis purposes. The DFE is a validated and widely used methodology for capturing micronutrient data in large populations and can be tailored for individual countries. It is expected that women use OCs for an average of approx. 3 to 4 years. Follow-up at 18 months would therefore be a good predictor of folate intake during OC use.

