Required women years in reference cohort	166,635	97,204
Total women years	179,178	110,460

Furthermore, 124,000 to 172,000WY of exposure would be sufficient to also exclude a twofold risk for ATE (cf. Table 4), assuming that 1) the incidence for DRSP/EE+ is comparable to the EURAS-OC results (~ 1/10,000) and 2) DRSP/EE+ accounts for at least 8% of the total exposure.

Table 4: Power calculation³² for ATE based on the assumption that the true incidence in the DRSP/EE+ cohort is ~ 1/10,000 compared to ~ 2/10,000 in the reference cohort.

Test significance level, α (one-sided)	0.025 (= 0.05 two-sided)	
ATE Incidence for reference cohort	2/10,000 WY	
Non-inferiority margin	2/10,000 WY (equal to twice the ATE incidence for the reference cohort)	
Expected ATE incidence for DRSP/EE+ cohort	1/10,000 WY	
Power (%)	90	
Proportion of DRSP/EE+ users (% of study population)	8	12
Required women years in DRSP/EE+ cohort	13,704	14,858
Required women years in reference cohort	157,594	108,953
Total women years	171,298	123,811

Evaluation Part II

For the primary outcome of interest (VTE/ATE), 90% power is taken as a basis. For the additional outcome of interest (colorectal cancer), a power reduction to 80% is also acceptable.

Power calculations for colorectal cancer are based on an incidence rate of 0.65/10,000WY. As a potential risk for colorectal cancer is associated with folate and not progestogen/estrogen combinations, the assessment of colorectal cancer will be based primarily on the combined COC+ cohort. For this cohort a proportion of 25-35% of the total study population is expected (see above). Based on a proportion of 35% and 25% approx. 531,000 and 644,000 WY of observation, respectively, are needed to exclude a two-fold risk of colorectal cancer (cf. Table 5). i.e., if the proportion should be 25%, it might be necessary to extend the follow-up period by one year as proposed in Table 1b. The final decision on the timely line of the INAS-FOCUS study should be made by the Safety Monitoring and Advisory Council after analysis of the incidence data within this study and discussion of the appropriate measures.

Table 5: Power calculation^{32 33} for colorectal cancer based on the assumption that the true incidence in the COC+ cohort is not different from the reference cohort.

Test significance level, α (one-sided)	0.025 (= 0.05 two-sided)	
Colorectal cancer incidence for reference cohort	0.65/10,000WY	

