Non-inferiority margin	0.65/10,000WY (equal to the colorectal cancer incidence for the reference cohort)	
Expected colorectal cancer incidence for COC+ cohort	0.65/10,000WY	
Power (%)	80	
Proportion of COC+ users (% of study population)	25	35
Required women years in COC+ cohort	160,993	185,761
Required women years in reference cohort	482,977	344,984
Total women years	643,970	530,745

These power calculations suggest that this study is sufficiently powered to show non-inferiority of COC+ compared to established OCs. However, exact power calculations based on actual incidences and drop-out rates should be done on the basis of two years follow-up data. If these calculations do not confirm the assumed incidences and drop-out rates the independent Safety Monitoring and Advisory Council (SMAC) may discuss the need for adapting patient numbers and follow-up times.

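### Section 11 decides colorectal cancer on as-treated time, Table 5 powers it on all observation time; if as-treated means current use, the stated 80% power is not reached

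*Protocol*

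**What the plan says.** Section 11 plans both as-treated (AT) and intention-to-treat (ITT) Cox analyses and then ranks them: "The safety conclusions of the study, however, will be based on the AT analyses because the ITT approach potentially dilutes differences between treatments". No outcome is excluded from that sentence. The section goes on to list confounders for CRC and adds: "Similar analyses will be performed for arterial thromboembolism (e.g., acute myocardial infarction and stroke), colorectal cancer and other serious adverse events".

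Section 12, Evaluation Part II, sizes CRC on a different time base. For COC+ shares of 35% and 25%, "approx. 531,000 and 644,000 WY of observation, respectively, are needed to exclude a two-fold risk of colorectal cancer". That requirement is set against the total observation time of Tables 1a and 1b (620,684 and 648,232 WY), and the optional extra year of follow-up is justified on the same basis. On power, "For the additional outcome of interest (colorectal cancer), a power reduction to 80% is also acceptable".

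Two other statements bear on how much of that time is exposed. Section 7 says: "It is expected that women use OCs for an average of approx. 3 to 4 years". Section 5 keeps women in follow-up after they stop the pill. Section 12, Evaluation Part I, takes about 4/5 of observed time at year 5 as exposure and turns 232,000 WY into about 185,000 WY before comparing with the cardiovascular requirement. Part II has no such step.

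**The concern.** The analysis that decides a conclusion and the calculation that says it is powered should count the same person-time. For venous thromboembolism (VTE) and arterial thromboembolism (ATE) they do: requirement and supply are both put in exposed WY. For CRC, Table 5 is met only by counting all follow-up, while section 11 read literally lets the AT analysis decide.

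Section 17 places the final evaluation of colorectal and other cancers at year 15, and section 1 presents the lack of long-term data on folate in this population as a reason for the study. If AT means current use, the time after stopping that Part II goes on collecting does not enter the deciding CRC analysis, and the protocol's statement that the study is sufficiently powered for CRC is not backed by its own figures.

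**Working it through.** **Inputs.** One-sided α 0.025 (Table 5); CRC incidence λ = 0.65/10,000 WY in both cohorts, and a margin of the same size as a rate difference (Table 5); COC+ share q = 25% or 35% (section 12); 80,000 women recruited over 3 years; annual drop-out 10% in follow-up years 1–5, 7% in years 6–10, 5% thereafter (section 12); exposure share 4/5 at year 5 (Part I); mean use 3 to 4 years (section 7).

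**Formula.** With equal rates and a margin equal to the rate, a total of W women-years gives power = Φ(√(λ·W·q·(1−q)) − 1.96).

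**Reproducing Table 5.**
- q = 0.25, W = 643,970: λW = 41.86; × 0.1875 = 7.85; root 2.80; Φ(0.84) = 80%.
- q = 0.35, W = 530,745: λW = 34.50; × 0.2275 = 7.85; root 2.80; Φ(0.84) = 80%.

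Table 5 is arithmetically right for the time base it uses. On all planned observation (620,684 WY) power is 78.5%/85.8%; with the extra year (648,232 WY) it is 80.3%/87.2%.

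**Exposed time if AT means current use (assumption).**

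(a) *Calibrated to the protocol's 4/5.* Let S(t) be retention under the planned drop-out, entry uniform over 3 years, and duration of use exponential with mean m (assumption). Exposed WY up to calendar year T = 80,000 × the average over entry time u of ∫₀^(T−u) S(t)·exp(−t/m) dt. Without the exponential term the model gives 231,972 WY at year 5 (Table 2: 232,272) and 613,786 at year 15 (Table 1a: 620,684), so it tracks the protocol's tables. An exposure share of 4/5 at year 5 requires m ≈ 7.3 years. Exposed time is then 185,577 WY at year 5 and 326,601 WY at year 15, or 326,601/620,684 = 53% of planned observation.

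(b) *Section 7's mean use, no drop-out.* 80,000 × 3 = 240,000 WY; 80,000 × 4 = 320,000 WY (39% and 52%).

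(c) *4/5 held throughout.* 0.8 × 620,684 = 496,547 WY. With the extra year, 0.8 × 648,232 = 518,586 WY.

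**Power on the plan's formula**, taking the COC+ share of exposed time as equal to its share of the cohort:

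| Time base | WY | Expected CRC (λW) | Power, 25% | Power, 35% |
|---|---|---|---|---|
| All observation, Table 1a | 620,684 | 40.3 | 78.5% | 85.8% |
| (a) 4/5 at year 5 | 326,601 | 21.2 | 51% | 59% |
| (b) 3 years' use | 240,000 | 15.6 | 40% | 47% |
| (b) 4 years' use | 320,000 | 20.8 | 51% | 58% |
| (c) 4/5 for 15 years | 496,547 | 32.3 | 69% | 77% |
| (c) with extra year | 518,586 | 33.7 | 71% | 79% |

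Every exposed-time scenario falls short of both Table 5 requirements and of 80% power. In the calibrated case, expected COC+ cases at a 25% share are 0.25 × 21.2 = 5.3, against 0.25 × 40.3 = 10.1 on all observation.

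**The case against.** The strongest reply is that the protocol never defines AT person-time. Carry-over, ever-exposed and lag rules are ordinarily left to the analysis plan, which section 11 promises. The AT sentence also comes soon after the VTE hypothesis; the extension to CRC comes a paragraph later and could refer only to the modelling approach; and Part II speaks of observation for CRC. On that view the two sections are unreconciled and no power has been lost. This stands in part: the loss is conditional on what AT means. It does not remove the point, because section 11 gives cancer no exception and Part I shows that observation and exposure were treated as different quantities. ITT results will be reported too, but section 11 says they do not decide.

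It can also be said that CRC is not the primary variable, that its power was deliberately relaxed to 80%, and that the advisory council may revisit incidence, drop-out, numbers and follow-up time. All true, but none of those reviews addresses the time base. Finally, low power in a non-inferiority comparison makes a twofold risk harder to exclude; it does not by itself create false reassurance. That is right: the risk is an unanswered question.

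**Conclusion.** The point holds as an inconsistency between section 11 and section 12, Part II. Table 5's arithmetic is correct; its person-time does not match the analysis named to decide. If AT is current-use time, CRC power at 25%/35% share is about 51%/59% in the case calibrated to the protocol's exposure share, 40–51%/47–58% on section 7's mean use, and 69%/77% on the most generous assumption, against 80% stated. These figures rest on the current-use reading of AT, on exponential duration of use in the calibrated case, and on equal COC+ shares of exposure and cohort. The VTE evaluation is not affected.

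A reader might infer more than the documents support:

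- *That most follow-up is discarded.* In the calibrated case 53% is kept.
- *That years 6–15 add almost nothing.* In that case they supply (326,601 − 185,577)/326,601 = 43% of exposed time.
- *That exposure is only 183,000–226,000 WY and power 32–38% at a 25% share.* This comes from exponential use with mean 3–4 years plus drop-out. It implies 140,000–157,000 exposed WY at year 5, against the protocol's 185,000, so it is not relied on.
- *That a folate effect could not appear during use.* Section 1 raises possible promotion of existing tumours, which could.
- *That power is lower still on the hazard ratio scale.* On all 620,684 WY it would already be about 48%/56%, from Φ(ln 2 × √(λWq(1−q)) − 1.96). Much of that gap is a separate matter of how the margin is expressed.

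**What to change.** In section 11, limit the sentence that rests conclusions on AT to VTE and ATE. For CRC and other cancers, name a deciding analysis whose person-time matches Table 5 and keeps time after stopping. One example is time-dependent ever-use of COC+: a woman enters the COC+ group at first COC+ use and stays there. A latency lag is an option, not a necessity. Keep AT and ITT as sensitivity analyses.

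If AT is to decide CRC after all, define its person-time and restate the power in Table 5 and the Part II text for expected exposed WY, with the exposure share assumed beyond year 5.

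The cost is wording in the protocol and analysis plan; section 5 already provides for collecting dates of discontinuation and switching. The downside is that ever-use may dilute an effect confined to current use, which the AT sensitivity analysis would address.
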